1 PROTOCOL SUMMARY

1.1 SYNOPSIS

Title:	Investigating Central Neurophysiologic Correlates of Non-motor Symptoms of Parkinson's Disease
Study Description:	This is a randomized, single-blinded, triple crossover study with 3 one-day iTBS, separated by a wash-out period of 3 weeks ¹ , sufficient for physiologic effects of one session of iTBS to return to baseline. Participants will undergo accelerated iTBS to 3 brain regions: medial prefrontal cortex (mPFC) (experimental site), dorsolateral prefrontal cortex (DLPFC) (alternative experimental site), or primary sensory cortex (S1) (control site). Participants will complete symptom questionnaires, neurologic examination and cognitive assessments, and orthostatic vital signs recording before and after each brain stimulation session.
Objectives:	

Primary Objective: Aim 1: To determine whether iTBS to the medial prefrontal cortex (mPFC) produces more robust changes in frontal midline theta (FMT) EEG power in people with Parkinson's disease compared with stimulation at the dorsolateral prefrontal cortex (DLPFC) or the primary sensory cortex (S1). Aim 2: A. To evaluate FMT power correlations with burden of autonomic symptoms in Parkinson's

disease. B. To evaluate FMT power correlations with burden of depression symptoms in Parkinson's disease

Exploratory Objectives:

Aim 3: To evaluate the effect of iTBS on autonomic symptoms one day after, and 4 days after stimulation. Aim 4: To evaluate the effect of iTBS on depression symptoms one day after, and 4 days after stimulation.

Aim 5: To create a database of EEG and TMS data in people with PD for the purpose of future research into novel neurostimulation therapies for PD NMS

Outcome measures:

Primary Outcome Measures: Aim 1: Degree of change of frontal midline theta power on EEG after brain stimulation. Aim 2: Degree of association between autonomic symptoms and frontal midline theta EEG power; Degree of association between depression symptoms and frontal midline theta EEG power.

Exploratory Outcome measures: Aim 3: Change in SCOPA-AUT and OHQ from before to after iTBS; Aim 4: Change in BDI-II from before to after iTBS

Study Population:

Study population will be men and women of all demographic groups with Parkinson's disease age 50-90 years who do not have a diagnosis of severe dementia who reside in North Carolina.

Phase:

N/A (pilot study)

Description of

UNC Medical Center will be the only participating site.

Sites/Facilities Enrolling

Participants:

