6.1.1.2 PREPARATION AND ADMINISTRATION OF STUDY INVESTIGATIONAL PRODUCT

After participants have completed questionnaires and EEG, they will be comfortably seated. The researcher will be thoroughly trained in the safe use of TMS. All researchers administering TMS have written and digital documentation of training. Researchers will be present at all times during stimulation. To monitor side effects of stimulation, a questionnaire will be administered after each stimulation session.

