Clinical Evaluations: The SCOPA-AUT⁵², a validated questionnaire for autonomic symptoms in PD, and the Orthostatic Hypotension Questionnaire (OHQ)⁵³, a validated questionnaire for symptoms of orthostatic

intolerance, will be administered before, and then by telephone one day after, and four days after each stimulation session. The Beck Depression inventory II (BDI-II)⁵⁴, recommended for screening and assessment of depression severity in PD⁵⁵, will be administered before, and then by telephone one day after, and four days after each stimulation. A trained research team member will administer the Movement Disorders Society Unified Parkinson Disease Rating Scale (MDS-UPDRS)⁵¹, a validated rating scale of PD symptom severity, at baseline. Participants will have orthostatic blood pressure measurement with a standard sphygmomanometer cuff before and after each stimulation session. All evaluations will be done with subjects in the “on” medication state with regards to dopaminergic medication dosing. Quantitative EEG (qEEG) recordings will be done before and immediately after each stimulation session. EEG: A high-density EEG net (128 electrodes including electrooculography electrodes; MagStim EGI, Inc.) and two submental electromyography (EMG) electrodes will be applied. Continuous qEEG recording will be performed for 8 minutes while the participant is asked to keep their eyes open and focused on a crosshairs. Sampling rate during the continuous recording will be 1 kHz with Cz as the reference and a channel between Cz and Pz as ground, using an EGI system with SDK AmpServer Pro (Geodesic, Eugene, Oregon). Intermittent theta-burst stimulation: Subjects will undergo iTBS to the mPFC, left DLPFC, and left primary sensory area in a triple cross-over study design. I will use a MagVenture MagPro X100 TMS device with active cooling coil. Stimulation location will be determined using established scalp coordinates for each stimulation location with the “10-20” international coordinate system⁴²⁻⁴⁵. For the mPFC, stimulation will be done at the Fp1 EEG electrode location, which can be calculated as along the midline of the scalp and 10% of the distance from nasion to inion. For left DLPFC, stimulation will be done at the F3 location using the Beam-F3 technique^{46,47}. For the primary sensory cortex, stimulation will be done 1.5cm posterior to the motor hotspot used for intensity calibration. Stimulation will be delivered at 80% active motor threshold. Accelerated iTBS will be performed in the reclined position to reduce symptoms of orthostatic hypotension, with subjects awake and at rest. Subjects will receive bursts of 3 pulses at 50 Hz repeated at 200-msec intervals (5Hz) for two seconds^{48,49}. The two-second trains will be repeated 20 times every 10 seconds (4 minutes total stimulation time), and followed by a 20 minute rest period. This sequence will be repeated 4 times. Behavioral effects of stimulation last at least 36 hours after one stimulation session with this protocol¹. TMS is FDA-approved for the treatment of symptoms of depression, and is a widely-used safe clinical tool.

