
6.1.3 DOSING AND ADMINISTRATION

During the first stimulation session in the study, participants will receive a motor thresholding procedure in which electrodes are attached to the first dorsal interosseous muscle of the right hand, or another muscle on the hand or arm that is accessible to be targeted by TMS to the motor cortex. The contralateral motor cortex will be targeted by single pulses of TMS with increased stimulator output until a motor evoked potential (MEP), defined as a near-instantaneous increase in muscle activity greater than 200 microvolts, is generated. Next, the intensity of single pulse TMS will be lowered until a MEP is generated on five out of 10 pulses. This is defined as the individual’s motor threshold. If MEP determination of motor threshold is not possible, the researcher will use visible twitches as a proxy for MEP. Participants will receive iTBS at 80% of their motor threshold.

Subjects will undergo iTBS to the mPFC, left DLPFC, and left primary sensory area in a triple cross-over study design. I will use a MagVenture MagPro X100 TMS device with active cooling coil. Stimulation

location will be determined using established scalp coordinates for each stimulation location with the “10-20” international coordinate system⁴²⁻⁴⁵. For the mPFC, stimulation will be done at the Fp1 EEG electrode location, which can be calculated as along the midline of the scalp and 10% of the distance from nasion to inion. For left DLPFC, stimulation will be done at the F3 location using the Beam-F3 technique^{46,47}. For the primary sensory cortex, stimulation will be done 1.5cm posterior to the motor hotspot used for intensity calibration. Accelerated iTBS will be performed in the reclined position to reduce symptoms of orthostatic hypotension, with subjects awake and at rest. Subjects will receive bursts of 3 pulses at 50 Hz repeated at 200-msec intervals (5Hz) for two seconds^{48,49}. The two-second trains will be repeated 20 times every 10 seconds (4 minutes total stimulation time), and followed by a 20 minute rest period. This sequence will be repeated 4 times. Behavioral effects of stimulation last at least 36 hours after one stimulation session with this protocol¹.

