6.2 MEASURES TO MINIMIZE BIAS: RANDOMIZATION AND BLINDING

To control for bias, we have decided on a prospective, controlled, triple crossover (three stimulation locations at separate study visits) study design. Participants will be blinded as to stimulation location, and each participant will experience stimulation at all locations. Each participant will have all rating scales performed by the same rater. Potential confounding factors, such as age, disease duration, cognitive function, and overall disease severity will be evaluated and controlled for, as indicated, in the final statistical models.

Stimulation order will be randomized and counter-balanced. Participants are assigned a study ID number and randomized upon signing the informed consent form. Subject ID will be entered into the randomization algorithm by the research assistant. A randomization table will be generated by a computerized script that randomizes and counterbalances by ID, generating an Excel spreadsheet. We will perform complete counterbalancing, there are 6 potential sequences (mPFC-DLPFC-S1, mPFC-S1-DLPFC, DLPFC-mPFC-S1, DLPFC-S1-mPFC, S1-mPFC-DLPFC, S1-DLPFC-mPFC) and a plan for 48 participants. Every effort will be made to completely counterbalance our sample. Thus effects of stimulation order will be minimized.

Treatment Assignment Procedures: Participants will receive stimulation to the medial prefrontal cortex, the dorsolateral prefrontal cortex, and the primary sensory cortex. The order of stimulation will be randomized and counterbalanced. Randomization will be performed using a script that generates a

spreadsheet. Randomization will be done after the screening visit is completed, before initiation of stimulation sessions.

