9.4 STATISTICAL ANALYSES

9.4.1 GENERAL APPROACH

All data are double entered by independent keyboard operators, compared to identify discrepancies, then reconciled with the data manager. All datasets are backed up daily. Linear mixed models with repeated measures across different regions or over time will be the primary analytic tool for testing our *a priori* hypotheses. To model correlation among repeated measures, we will primarily consider either random intercept or AR(1). We will use the likelihood ratio test (or Wald test) statistic to test

the hypotheses. We will appropriately handle missing data (e.g., missing responses and/or covariates) by using imputation or other methods. To identify significant component terms in each of the models, we will examine the parameter estimates, 95% confidence intervals, and p-values of the component terms in an analysis of fixed effects for the final mixed models. Before undertaking statistical modeling, we will perform descriptive analyses and examine the distributions of all measures. Appropriate transformations or nonparametric statistical tests will be considered if necessary. **All statistical estimates of population parameters will be tabulated along with corresponding confidence intervals (CIs) and/or standard errors (SEs) to convey levels of precision / imprecision.** Following is a detailed plan for testing each hypothesis and the power assessment when feasible.

Descriptive statistics: Categorical data (sex) will be presented as percentages. Continuous data (age, disease duration, scores on SCOPA-AUT, OHQ, BDI-II, MDS-UPDRS all parts, freezing of gait questionnaire, Epworth Sleepiness scale, REM sleep behavior disorder questionnaire, and MoCA, will be presented as means with standard deviation and range.

Primary analysis, Aim 1: To test the degree of change in the power of FMT before and after iTBS at each location, we will use linear mixed models with FMT being the dependent variable. We will primarily include stimulation location (mPFC, DLPFC, S1), time (before, after stimulation), and the interaction term Location*time in the model.

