Primary Analysis, Aim 2: 1. To test associations of autonomic symptoms in PD subjects with FMT, we will use linear regression modeling. The dependent variable will be FMT, whereas primary covariates will be SCOPA-AUT, OHQ score, and magnitude of systolic blood pressure reduction during orthostatic blood pressure measurement. We will further use linear regression models to examine the associations between depression symptoms in PD subjects and FMT, using linear regression modeling. **Exploratory Analyses:** 1. We will use linear mixed models to examine the effect of iTBS on autonomic symptoms one day after, and 4 days after stimulation. SCOPA-AUT and OHQ will be the dependent variable in the ANOVA analysis. The factors will be stimulation location (mPFC, DLPFC, S1) by time (before and after). 2. Similarly, we will use linear mixed models to evaluate the effect of iTBS on depression symptoms one day after, and 4 days after stimulation. BDI-II will be the dependent variable, whereas the primary factors will be stimulation location (mPFC, DLPFC, S1) by time (before and after). **In all statistical models,** Some key confounding factors (age, disease duration) will be controlled in both linear mixed effects and regression models. **Post-hoc analysis** will be performed using Tukey's method to control for multiple comparisons.

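### The Aim 1 model has no visit term although Visit 1 differs by design; a visit effect on the FMT change, if present, would widen the reported error and, with unequal sequences, bias the site contrast

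*Combined protocol and SAP*

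**What the plan says.** **Model.** Section 9.4.1 names the Aim 1 terms: "We will primarily include stimulation location (mPFC, DLPFC, S1), time (before, after stimulation), and the interaction term Location*time in the model". Within-participant correlation is to be a random intercept or AR(1). On covariates it adds: "Some key confounding factors (age, disease duration) will be controlled in both linear mixed effects and regression models". Both are fixed characteristics of the participant. No section names a visit, period, sequence or carry-over term.

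**Order.** Section 6.2 plans complete counterbalancing of six sequences over 48 participants, presents exact balance as a goal, and concludes: "Thus effects of stimulation order will be minimized".

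**Visit 1.** Sections 4.3 and 6.1.3 place thresholding, a series of single TMS pulses, at one visit: "During the first stimulation session in the study, participants will receive a motor thresholding procedure". Section 6.1.1.2 says: "After participants have completed questionnaires and EEG, they will be comfortably seated". That suggests the EEG precedes the TMS set-up, but the order of thresholding and the pre-session EEG is not stated.

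**Wash-out.** The synopsis calls three weeks "sufficient for physiologic effects of one session of iTBS to return to baseline", with a citation. Elsewhere the same reference supports this: "Behavioral effects of stimulation last at least 36 hours after one stimulation session with this protocol".

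**The concern.** In a three-period crossover, anything that makes one visit's response differ from the others is a period effect. Here there is a concrete candidate: only the first session includes thresholding, and TMS is new to the participant then. If that alters the same-day FMT change, which is the Aim 1 outcome, the named model cannot absorb it, because age and disease duration do not vary between a participant's visits.

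Counterbalancing protects the estimate only while sequences are equal, and even then the visit effect is counted as residual noise. At stake are the width of the reported interval, the power of the test and, under imbalance, the estimate itself. A secondary matter is that the plan never checks whether each visit starts from baseline, although EEG and questionnaires are collected before every session.

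**Working it through.** **The plan's own figure.** Section 9.2 gives Aim 1 power of 0.82 with f² = 0.15, N = 45, 3 predictors and alpha 0.05. As a one-sided test of a single coefficient, λ = 0.15 × 45 = 6.75 with 45 − 3 − 1 = 41 df, and power is 0.819, so the figure reproduces. (The two-sided version gives 0.718.) The calculation says nothing about visit effects.

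**Inputs.** 48 participants, 6 sequences, so 8 per sequence (6.2); EEG before and after each session (6.1.2); model terms from 9.4.1. Assumed, because the documents give no value: a Visit 1 shift in the before-to-after change of d = 0.5, 1.0 or 1.5, in units of the residual SD of one visit's change.

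**1. Exact balance, model as in 9.4.1 with a random intercept.** There are 48 × 6 = 288 observations. Participants take 48 parameters, and location, time and their interaction take 5, leaving 235 residual df. With independent residuals, the SD of a change is √2 times the SD of one observation, so a shift of d is √2·d on the observation scale. It occurs at one of six observations. After participant and time effects are removed, each participant contributes (5/6 − 1/6) × 2d² = (4/3)d² to the residual sum of squares; at balance, location absorbs none. The total is 64d².

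SE ratio = √(1 + 64d²/235).

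**2. Exact balance, change scores with participants as blocks.** 144 − 48 − 2 = 94 df, and the extra residual sum of squares is 48 × (2/3)d² = 32d².

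SE ratio = √(1 + 32d²/94).

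| d | SE ratio, 9.4.1-type model | SE ratio, change scores | Power, 9.4.1-type | Power, change scores |
|---|---|---|---|---|
| 0 | 1.00 | 1.00 | 0.80 | 0.80 |
| 0.5 | 1.03 | 1.04 | 0.78 | 0.78 |
| 1.0 | 1.13 | 1.16 | 0.72 | 0.70 |
| 1.5 | 1.27 | 1.33 | 0.62 | 0.57 |

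Power is for a contrast that has 80% two-sided power when visit is modelled. It equals Φ(c + 0.842 − c × ratio), with c = 1.970 (235 df) or 1.986 (94 df). At d = 1.0 under 9.4.1, that is Φ(2.812 − 2.222) = 0.72.

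The estimate is the same with or without the visit terms, and so is its true sampling error, √(2/48) = 0.204 SD. Only the reported SE grows. The nominal 5% test then rejects a true null in about 4%, 3% and 1% of trials under the 9.4.1-type model, for example 2 × (1 − Φ(2.222)) = 0.026 at d = 1.0.

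**3. Unequal sequences.** Without visit terms, the bias in a site contrast is d times the difference between the two sites' proportions of first visits. At N = 45, 45/6 = 7.5, so equal sequences are impossible. If all three losses come from mPFC-first sequences, first visits number 13, 16 and 16, and the bias is d × 3/45: 0.033 SD at d = 0.5 and 0.067 SD at d = 1.0, against an SE of about 0.21. With nine such losses it is d × 9/39: 0.115 and 0.231 SD.

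**4. Which term removes it.** Fitting the 45-participant case in the six-observation model at d = 0.5 leaves the bias at 0.033 SD with a visit main effect added, and reduces it to 0 with visit x time. A Visit 1 shift common to both EEGs cancels from Location*time: the bias is 0 even at N = 39, and only the SE rises.

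**The case against.** The case for leaving the model alone has weight. Randomised complete counterbalancing is planned and, if achieved, removes the bias. Calling the listed terms primary leaves room for others. The trial is labelled a pilot. No document gives evidence of a visit effect, and shifts of 1.0 to 1.5 SD would exceed the site difference detectable with 80% power: 2.83 × 0.204 = 0.58 SD. At 0.5 SD the power loss is about two percentage points. The route through thresholding is also inferred: if thresholding precedes the pre-session EEG and acts equally on both recordings, it cancels.

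All of this limits the size of the point. It does not remove it. Room for further terms is not pre-specification. Balance is a goal, and section 7.2 says participants who withdraw after receiving stimulation are not replaced.

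A reader might infer that the site comparison will lose precision or be biased. The documents do not support that: the first harm needs a visit effect, the second also needs unequal sequences, and at exact balance the estimate itself loses nothing. A reader might also infer that the wash-out claim is unsupported or that carry-over contaminates Aim 1. The synopsis does cite a source, which cannot be examined here, and additive carry-over present at both EEGs of a visit largely cancels from the same-day change.

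**Conclusion.** The point holds conditionally. The named Aim 1 model has no term for visit, the visits differ by design, and counterbalancing is the only protection. Given a Visit 1 effect on the FMT change of 0.5, 1.0 or 1.5 SD, the reported SE at exact balance is about 3%, 13% or 27% too wide (4%, 16% or 33% with blocked change scores) and the test is conservative, while the estimate stays unbiased. Given unequal sequences as well, three losses confined to mPFC-first sequences produce a bias of 0.03 to 0.07 SD for shifts of 0.5 to 1 SD; larger bias needs heavier one-sided loss. The shift sizes are assumptions, and the SE figures for the planned model assume a random intercept with independent residuals.

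On the wash-out, the only duration the documents give is a minimum, 36 hours, and it concerns behavioural effects. A lower bound cannot show that physiologic effects have gone by three weeks, so this is an assumption that can be checked. It is secondary to the visit terms.

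**What to change.** In 9.4.1, add visit number (1, 2, 3) and visit x time as fixed effects to the Aim 1 model, and do likewise in the Aim 3 and Aim 4 models. Specify both terms, because the main effect alone leaves the bias in place.

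As a sensitivity check, compare pre-session FMT, BDI-II, SCOPA-AUT and OHQ at Visits 2 and 3 with Visit 1, by preceding stimulation site. Reword the synopsis to say that three weeks is assumed to be long enough and that this will be checked.

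The cost is wording plus four degrees of freedom (two for visit, two for visit x time), which takes the residual df from 235 to 231 in the calculation above. There are no new data and nothing changes for participants. If there is no visit effect, power is essentially unchanged. The terms should be fixed before results are seen.

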8.1.2 OBJECTIVE EVALUATIONS

Participants will undergo the following disease rating scales and cognitive examination evaluations prior to stimulation:

- The MDS UPDRS part Ia - this is a questionnaire, administered by the investigator, and consists of 6 question, each scored 0-4 points. Score range is 0-24. It takes 10 minutes to administer⁵¹. This will be completed at the screening visit
- MDS UPDRS part III – this is the neurological examination portion of the MDS UPDRS, and takes about 10 minutes to complete⁵¹. Each question is scored 0-4. Score range is 0-132, with higher score indicating higher burden of motor symptoms. This will be completed at the screening visit
- The MDS UPDRS part IV – this is the dyskinesia rating portion. It consists of 6 questions, each scored from 0-4 points and takes 10 minutes to complete⁵¹. Score range is 0-24. This will be completed at the screening visit.

- MoCA – Montreal Cognitive Assessment. This is a neurocognitive screening tool, and takes about 15 minutes to administer⁵⁰. The visuospatial/executive function portion consists of three questions with a score range of 0-5; the naming portion consists of three questions with a score range of 0-3; the attention portion consists of 4 questions with a score range of 0-6; the abstraction portion has 2 questions and has a score range of 0-2; The delayed recall is one question and is scored 0-5 points; and orientation is 6 questions with a score range of 0-6 points. The total score range is 0-30, where lower score indicates higher burden of symptoms. This will be completed at the screening visit.
- Participants will undergo EEG before and immediately after brain stimulation. A high-density EEG net (128 electrodes including electrooculography electrodes; MagStim EGI, Inc.) and two submental electromyography (EMG) electrodes will be applied. Continuous EEG recording will be performed for 8 minutes while the participant is asked to keep their eyes open and focused on a crosshairs. Sampling rate during the continuous recording will be 1 kHz with Cz as the reference and a channel between Cz and Pz as ground, using an EGI system with SDK AmpServer Pro (Geodesic, Eugene, Oregon). EEG frequency will be reported in Hz. The primary outcome measure, FMT power, will be reported in μ .

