9.4.7 SUB-GROUP ANALYSES

Associations between the covariates of gender, age, and disease duration with the dependent and independent variables will be evaluated. Covariates will be accounted for in ANCOVA or linear regression models, respectively.

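### Aim 1 tests the site contrast through Location*time without adjusting for the pre-session FMT reading: valid, but less precise than the collected data allow

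*Combined protocol and SAP*

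**What the plan says.** Section 9.4.1 states for Aim 1 that "we will use linear mixed models with FMT being the dependent variable", and then: "We will primarily include stimulation location (mPFC, DLPFC, S1), time (before, after stimulation), and the interaction term Location*time in the model". The dependent variable therefore covers both readings, and the location term leaves the pre-session mean free to differ by site. The same section offers a random intercept or AR(1) for the correlation among repeated measures.

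Pre-session FMT is not named as a covariate anywhere:

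- Section 9.4.1: "Some key confounding factors (age, disease duration) will be controlled in both linear mixed effects and regression models".
- Section 6.2: "Potential confounding factors, such as age, disease duration, cognitive function, and overall disease severity will be evaluated and controlled for, as indicated".
- Section 9.4.7, which mentions ANCOVA: "Associations between the covariates of gender, age, and disease duration with the dependent and independent variables will be evaluated".
- Sections 9.4.2 and 9.4.3 only refer back to 9.4.1.

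The data and design needed for baseline adjustment are in place. Section 8.1.2: "Participants will undergo EEG before and immediately after brain stimulation". Section 6.2: "Stimulation order will be randomized and counter-balanced", over all six sequences. The synopsis (1.1) sets a 3-week wash-out and regards it as long enough for the effects of one session to disappear.

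**The concern.** Because order is randomized over six balanced sequences, pre-session FMT should have the same expected value before each site, provided nothing carries over. The plan nevertheless estimates a separate pre-session mean for each site and subtracts it. The visit-to-visit noise in the pre-session reading then enters the primary contrast in full.

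The covariates that are named do not help. Age and disease duration are constant within a participant, so they explain none of the within-participant variation on which a crossover contrast rests. Pre-session FMT varies within participant and could explain some of it.

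What is at stake is precision. Section 9.2 says there are no preliminary data for the Aim 1 effect size, the sample is set at 48, and reaching it means pre-screening 400 people and screening 90.

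**Working it through.** **The plan's own power figure.** Section 9.2 gives power 0.82 for N = 45, f² = 0.15, alpha 0.05 and 3 predictors. A t test of one regression coefficient has noncentrality √(0.15 × 45) = √6.75 = 2.598 and 45 − 3 − 1 = 41 degrees of freedom. One-sided power is 0.819, which reproduces 0.82; two-sided it is 0.718. The documents do not state sidedness. This regression f² does not map directly onto the Location*time contrast, so it serves below only as an illustration.

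**Variance of the site contrast.** Remove the participant mean. Let s² be the variance of a single reading within participant and rho the same-visit before/after correlation (assumed; not in the documents).

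- Raw change: Var(after − before) = 2s²(1 − rho).
- Adjusted: Var(after | before) = s²(1 − rho²).
- Ratio: (1 − rho²) / [2(1 − rho)] = (1 + rho)/2.

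A pairwise site contrast over 48 complete participants has twice these variances divided by 48. With s² = 1:

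| rho | Raw change, 4(1−rho)/48 | Adjusted, 2(1−rho²)/48 | Ratio | 48 / ratio | Simulated power, raw → adjusted |
|---|---|---|---|---|---|
| 0.3 | 0.0583 | 0.0379 | 0.65 | 73.8 | 0.38 → 0.52 |
| 0.5 | 0.0417 | 0.0313 | 0.75 | 64.0 | 0.49 → 0.60 |
| 0.7 | 0.0250 | 0.0213 | 0.85 | 56.5 | 0.70 → 0.77 |
| 0.9 | 0.0083 | 0.0079 | 0.95 | 50.5 | 0.99 → 0.99 |

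The simulations used 48 participants, six sequences, period effects, fixed participant effects, an assumed site effect of 0.4 within-participant SD and a two-sided 0.05 test. Repeat simulations agreed to within about 0.02 in power. Simulated variance ratios were 0.65–0.67, 0.73–0.76, 0.86 and 0.96. With no carry-over, the adjusted model's type I error was 0.046–0.055 and its estimate was unbiased.

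**Under the plan's own covariance options.** These figures come from generalized least squares for the same design, comparing common pre-session means with free ones. A random intercept, which implies rho = 0 once the participant mean is removed, gives a ratio of 0.50. AR(1) gives 0.59, 0.64, 0.68 and 0.70 at AR parameter 0.3, 0.5, 0.7 and 0.9. Under AR(1) the planned interaction is not the raw-change contrast: it has 0.96, 0.91, 0.87 and 0.85 of the raw-change variance at those values. The (1+rho)/2 table therefore does not describe the plan under AR(1), although a loss remains there too.

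**Illustration on the stated power.** If 0.82 is taken to describe the Location*time contrast, dividing the noncentrality by √ratio gives one-sided power of 0.936, 0.904, 0.870 and 0.836 at rho 0.3, 0.5, 0.7 and 0.9.

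**A shortcut that fails.** Dropping the location main effect while keeping only a random intercept makes the estimator ignore the same-visit before reading. It then compares after readings alone. Its variance relative to raw change is s² / [2s²(1 − rho)] = 1/[2(1 − rho)]: 0.71, 1.00, 1.67 and 5.0 at rho 0.3, 0.5, 0.7 and 0.9. For rho above 0.5 that is worse than the plan.

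**Carry-over.** A site never follows itself. mPFC directly precedes DLPFC in 2 of the 6 sequences and never precedes mPFC. Suppose an mPFC after-effect c persists equally in both readings of the next visit. The mPFC − DLPFC difference in each reading then shifts by 0 − c/3. Raw change cancels the shift. The adjusted contrast keeps about (1 − rho) of it: at rho = 0.5, −c/6 = −0.17c. Simulation with c = 1 SD gave about −0.14 to −0.17.

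**The case against.** The strongest reply is that nothing here is an error. The Aim 1 hypothesis in section 9.1 concerns mean change, and Location*time tests exactly that without bias. The word "primarily" in 9.4.1 also leaves room for further terms. This stands, and a reader who inferred that the planned test is biased or invalid would be going beyond the documents. If anything, a random intercept alone overstates the standard error when rho is positive and makes the test conservative. Even so, leaving room for a term is not the same as specifying it.

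The second reply is that rho is unknown. Both readings come from one visit, so rho may be high and the gain small. This also stands: at 0.9 the saving is 5% of variance. It limits the size of the point, not its direction.

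The third is that equal pre-session means depend on complete wash-out, which randomized order alone does not guarantee. That is correct. Raw change is protected against an after-effect that is equal in both readings, and the adjusted contrast is not. The plan, however, already treats 3 weeks as sufficient.

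A reader might also extend the point to BDI-II, SCOPA-AUT and OHQ in Aims 3 and 4. The documents do not support this: those hypotheses ask whether change from pre-stimulation is zero at days 1 and 4, not whether sites differ.

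**Conclusion.** The point holds as one of efficiency, for the Aim 1 between-site contrast only. The planned analysis is valid but uses the pre-session reading less well than it could. Adjustment cuts the contrast variance to (1+rho)/2 of the raw-change value: by 35% at rho 0.3, 25% at 0.5, 15% at 0.7 and 5% at 0.9. This rests on complete data, a within-participant covariate slope, no carry-over after 3 weeks, and a planned model with a random intercept or visit-level effect.

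A reader might infer that the interaction equals raw change under any covariance structure, or that simply dropping the location term achieves the same gain. Neither follows: the first fails under AR(1), which the plan names, and the second fails under a random intercept alone. Nor do these figures show that the trial is underpowered, since neither rho nor the true effect is known. The change is worth making because it is cheap, not because the plan is unsound without it.

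**What to change.** In section 9.4.1, specify the Aim 1 between-site contrast as follows:

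- Model after-session FMT on location and visit (period), with that visit's before-session FMT as covariate and participant as a fixed effect.
- If participant is random instead, also include the participant's mean before-session FMT, so that the covariate slope is within-participant.
- A joint before/after model with common pre-session means is acceptable only if its covariance includes a same-visit before/after correlation. A random intercept alone is not enough.
- Keep the planned Location*time model to report change within each site and as a sensitivity analysis.
- Compare pre-session FMT by preceding site as a check on carry-over, and state that the adjusted contrast assumes there is none.
- Leave Aims 3 and 4 as they are on this point.

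The cost is SAP wording and one degree of freedom for the covariate. No new data are needed. The wording should be settled before outcome data are analysed. With participant fixed, age and disease duration drop out of this contrast, and a participant with usable readings from only one visit adds nothing to it.
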